1.2 Secondary Objectives

- a. To evaluate and compare response rates (RR) for each arm.
- b. To evaluate response rates (RR) for patients that relapse on low dose carfilzomib and subsequently cross-over to high dose carfilzomib.
- c. To evaluate the safety of this combination for this patient population.
- d. To evaluate overall survival (OS)

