5.2 Registration Step 2: Crossover

- a. Patient must have been eligible for and initially randomized to Arm 1 (low dose carfilzomib), begun Cycle 2 of treatment, and progressed prior to completing 12 cycles of protocol therapy.
- b. At least 14 days and no more than 28 days must have elapsed between the last day of treatment on Arm 1 and registration to Arm 3.
- c. Patients must have recovered from all non-hematologic toxicities to \leq Grade 2 and from all hematologic toxicities to \leq Grade 3 prior to registration.
- d. Patients must have begun Cycle 2 (carfilzomib - 27 mg/m²) and must not have received any dose reduction for toxicity in the last cycle of treatment, immediately preceding progression.
- e. Patients must have SPEP and kappa and lambda light chain testing performed within 14 days prior to registration in order to establish baseline measurements.
- f. Patients must not have ejection fraction decrease $> 10\%$ from baseline (as determined by ECHO), or other ejection fraction decrease accompanied by other clinical signs/symptoms of NYHA Class III or IV heart failure, measured within 28 days prior to registration. If any question exists regarding individual patient eligibility in this situation, contact the Study Chair for determination.

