7.1 General Considerations

- a. Patients must have creatine kinase (CK), cardiac-specific troponin T (TnT) and/or troponin I (TnI) testing—both TnT and TnI preferred if available, creatine kinase-MB (CK-MB), brain natriuretic peptide (BNP) and/or proBNP performed on Cycle 1, Day 1. See [Section 9.0](#) for additional timepoints. In the event that Cycle 1, Day 1 laboratory tests are resulted and the patient no longer meets one or more of the eligibility criteria, treatment must be held. Laboratory tests and any associated supportive care must be repeated. If the repeat lab results fall within the eligibility criteria, treatment may be resumed. In the event that treatment must be held for \geq 28 days, the patient must be removed from the protocol.
- b. Patients on Arm 1 will receive dexamethasone/low-dose carfilzomib for up to 12 cycles or until progression that occurs after the start of Cycle 2, whichever comes first. If patient progresses after the start of Cycle 2 and prior to completion of 12 cycles, the patient will cross-over and be registered to Arm 3 where they may receive up to an additional 12 cycles of treatment.
- c. Results of Day 1 laboratory tests are not required prior to starting treatment for each cycle subsequent Cycle 1 (see Section 7.1a for instructions regarding D1, C1 results). If lab results are abnormal or indicative of adverse events, the treating physician should refer to Section 8.0 for dose modifications, and Response Assessments should be conducted at time of dose modification and as indicated in [Section 9.0](#). If dose modification is not indicated, the physician should otherwise continue treatment at physician discretion.
- d. Patients on Arm 2 will receive dexamethasone/high dose carfilzomib for up to 12 cycles, or until progression that occurs after the start of Cycle 2, whichever comes first. If a patient progresses after the start of Cycle 2, the patient will discontinue protocol treatment.

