7.6 Criteria for Removal from Protocol Treatment

- a. Progression of disease or symptomatic deterioration (as defined in Section [10.5](#)) **for patients being treated with higher dose (56 mg/m²) carfilzomib.**
- b. Completion of 12 cycles of low dose carfilzomib on Arm 1 or 12 cycles of high dose carfilzomib.
- c. Unacceptable toxicity.
- d. Patient is unable to dose-escalate to assigned dose (27 mg/m² or 56 mg/m²) after 2 cycles of therapy.
- e. Permanent discontinuation of carfilzomib.
- f. Treatment delay for any reason > 4 weeks.
- g. The patient may withdraw from the study at any time for any reason.

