11.5 Analysis of Secondary Endpoints

Secondary efficacy endpoints include response rate (PR or better) and overall survival (OS). All efficacy analyses will be performed on intent to treat basis. The response rate (sCR, CR, VGPR, PR) for each arm will be determined by the number of patients achieving a response as defined in Section [10.3](#) divided by the number of patients assessed for response in each arm and compared between arms using Fisher's exact test.

The response rate for patients who relapse on Arm 1 and cross-over to Arm 3 will also be determined in order to determine whether response can be re-captured for those patients by increasing the carfilzomib dose.

Overall survival will be assessed in each arm using the method of Kaplan Meier and compared using the stratified log-rank test.

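### The single Arm 3 response rate can mix regained responses with first responses, so it does not by itself support the re-capture interpretation in Section 11.5

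*Combined protocol and SAP*

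**What the plan says.** Objective 1.2b is: "To evaluate response rates (RR) for patients that relapse on low dose carfilzomib and subsequently cross-over to high dose carfilzomib". Section 11.5 turns this into one sentence of analysis. It begins "The response rate for patients who relapse on Arm 1 and cross-over to Arm 3 will also be determined" and gives the purpose as "in order to determine whether response can be re-captured for those patients by increasing the carfilzomib dose". No split by Arm 1 outcome, expected number, reference rate or test is given for this rate.

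Entry to Arm 3 is set in Section 5.2. Criterion 5.2a asks that the patient was eligible for and randomized to Arm 1, and has "begun Cycle 2 of treatment, and progressed prior to completing 12 cycles of protocol therapy". Criterion 5.2d adds that patients "must not have received any dose reduction for toxicity in the last cycle of treatment". The remaining criteria cover timing since the last Arm 1 treatment, recovery from toxicity, ejection fraction and a new baseline: "Patients must have SPEP and kappa and lambda light chain testing performed within 14 days prior to registration in order to establish baseline measurements". Section 7.1b states the same trigger: "If patient progresses after the start of Cycle 2 and prior to completion of 12 cycles, the patient will cross-over and be registered". None of these asks for a response on Arm 1.

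At the other end, Section 7.6b lists among the reasons for leaving protocol treatment "Completion of 12 cycles of low dose carfilzomib on Arm 1 or 12 cycles of high dose carfilzomib".

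**The concern.** A response can be re-captured only if there was one to lose. Section 10.3 allows an Arm 1 best response of stable disease, or of increasing disease (progression as the first usable status, within eight weeks of registration). With 28-day cycles, Cycle 2 starts in week 5, so both kinds of patient can meet 5.2a. A PR on Arm 3 in such a patient is a first response, obtained at a higher dose in disease that had not responded to the lower one. In a patient who had a PR on Arm 1 and then progressed, it is a regained response.

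The protocol's background, in the part on resistance to carfilzomib, itself separates disease that comes back after an initial response from disease that is refractory from the start. Section 11.5 does not carry that distinction into the analysis. A low pooled rate could then be reported as failure to re-capture when it reflects primary resistance. A higher one could be reported as re-capture when some or all of the responses are first responses.

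**Working it through.** **The plan's own figures.** None is stated for the crossover rate. Its exponential model is used below, so the design figures that rest on it come first. Inputs from 11.2 and 11.3: medians of 9 and 15 months, 63 patients per arm, 1.75 years of accrual, 1.5 years of follow-up, one-sided alpha 0.1.

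- Expected events per arm = 63 × {1 − [exp(−1.5λ) − exp(−3.25λ)] / (1.75λ)}, with λ = ln 2 / (median in years). This gives 55.2 + 45.4 = 100.6, against a stated 100.
- Power at 100 events = Φ(√(100/4) × ln(15/9) − 1.282) = Φ(1.273) = 0.898, against a stated 90%.

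Both reproduce.

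**Upper limit for the crossover group.** Cycles last 28 days (7.3), so one cycle is 28/30.4375 = 0.92 months and twelve are 336/30.4375 = 11.04 months. With S(t) = exp(−ln 2 × t/9):

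- S(0.92) = 0.932, so 63 × (1 − 0.932) ≈ 4 events fall in Cycle 1.
- S(11.04) = 0.427, so 63 × (0.932 − 0.427) ≈ 32 events fall in Cycles 2-12.
- Events to the end of Cycle 12: 63 × (1 − 0.427) ≈ 36, or 57%.
- Event-free at the end of Cycle 12: 63 × 0.427 ≈ 27, or 43%.

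The upper limit is about 32 if the Cycle 1 events are left out and about 36 if all are counted. The real number is lower. A PFS event under 10.5 may be a death or symptomatic deterioration, and others are lost to toxicity, dose reduction (5.2d), the ejection-fraction rule (5.2f) or refusal.

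**What a pooled rate can show.** Let q be the share of crossover patients with no Arm 1 response, and let r_R and r_N be the Arm 3 response rates in prior responders and non-responders. Then pooled rate = (1 − q) × r_R + q × r_N. The documents do not give q, so 30% to 70% is assumed.

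| r_R / r_N | q = 30% | q = 50% | q = 70% |
|---|---|---|---|
| 40% / 0% | 28% | 20% | 12% |
| 20% / 20% | 20% | 20% | 20% |
| 0% / 40% | 12% | 20% | 28% |

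At q = 50% a pooled 20% fits all three rows, including one in which no response is regained. With r_R fixed at 40% and r_N at 0%, the pooled rate runs from 28% to 12% through the mix alone. These rows show what the arithmetic allows; they are not forecasts.

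**Precision (exact 95% intervals).** At a 50:50 split of 36 there are 18 per group. For example, 4/18 = 22% (6% to 48%). A pooled 7/36 = 19% has the interval 8% to 36%.

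**The case against.** The strongest reply is that the endpoint matches its objective. Objective 1.2b asks only for a response rate in crossover patients and does not mention re-capture. A reader might infer that the planned rate fails the secondary objective; it does not. The difficulty lies in the purpose clause in 11.5, which has no threshold or test attached. This part of the reply stands.

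A second reply is that relapse, read strictly, means loss of a response, so the analysis set is already prior responders. The text does not secure that reading. Relapse is nowhere defined, and Section 14.4e joins progression and relapse as a single reporting event. Under the strict reading there would also be a gap: crossover non-responders would have no planned analysis, and two analysts could use different denominators.

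Two stronger readings are tempting and should be resisted.

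- A reader might infer that shutting out patients who progress after 12 cycles also prevents the rate from answering its question. Section 11.5 concerns the patients who do cross over, and those who complete 12 cycles have left protocol treatment. Their absence limits generalisability and contradicts nothing.
- A reader might infer that the crossover group is weighted towards non-responders. That is plausible for early progressors, but no document gives the share.

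It is also fair that the rate is descriptive, and that the PFS, overall survival and Arm 1 versus Arm 2 response comparisons are unaffected.

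**Conclusion.** The concern holds in a limited form. As written, 11.5 yields a rate that describes crossover patients as a group. It does not by itself show whether a lost response can be regained, because entry to Arm 3 requires no Arm 1 response and the planned rate is not split by it.

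The group is small: at most about 32-36 of 63. That figure rests on the plan's exponential PFS with a 9-month median and is an upper limit, not an expected crossover count. How far the pooled rate could mislead depends on the mix of prior responders and non-responders, for which only assumed values can be shown. The consequence is confined to the interpretation of one untested secondary endpoint.

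**What to change.** In Section 11.5:

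1. Base the re-capture statement on crossover patients whose Arm 1 best response under 10.3 was PR or better: the number with PR or better on Arm 3 divided by the number of such patients.
2. Report the Arm 3 response rate separately for crossover patients without an Arm 1 response, and state in which group an unconfirmed Arm 1 response counts.
3. Give each rate an exact confidence interval.
4. Keep the pooled rate as the description that meets objective 1.2b.
5. State, as a limit on generalisability only, that the result applies to progression within 12 cycles on treatment.

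No entry or treatment rule changes. Arm 1 best response is already needed for objective 1.2a and comes from the tumor assessment forms submitted after each cycle (14.4b), so no new data are required. Fixing the split before the analysis also prevents a later choice of denominator. The cost is precision, as the 4/18 example shows; the narrower pooled interval belongs to a different question.

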11.6 Translational Medicine/Imaging Endpoints

GEP of the bone marrow plasma cells will be compared to that of an aspirate taken at the site of the EMP. Gene expression data will be log-transformed before any analysis. Exploratory analyses will be performed to examine the underlying distributions using boxplots, density plots, scatter plots, and so on. For differential expression analysis of the two sample types t-tests will be conducted upon tens of thousands of genes simultaneously. False discovery rate (FDR) will be used to control the average false positive proportions among selected genes. Genes will be ranked by their q-value and pathway analysis (www.ingenuity.com) will be conducted upon selected genes to ascertain biological plausibility and relevance to important molecular functionality.

Baseline PET images will be used to determine how many patients present with EMP. It is expected that 10-20% of patients (approximately 16-32 patients) will have EMP. For those patients, a second PET image will be taken when they achieve a VGPR or better, or at the end of their twelfth cycle of treatment, whichever is earlier. This second PET image will help determine response in those patients.

The main focus will be to determine the association of biochemical response with PET response for patients presenting with EMP at baseline. In this context a CR by PET will be defined by the disappearance of all focal lesions and the resolution of EMD. Univariate and multivariate logistic regression will be used to determine the impact of biochemical CR as defined in Section [10.1](#) on CR by PET. In the multivariate analysis adjustment for standard prognostic factors such as age, albumin, β -2 microglobulin, serum creatinine, CRP and LDH will be included.

In order to evaluate whether there is a difference in the incidence of clinically relevant cardiovascular toxicity, between treatment arms (normal- versus high-dose carfilzomib), where a clinically relevant cardiovascular toxicity is defined as the clinical development of any of the following toxicities per Common Terminology Criteria for Adverse Events version 4.0 (CTCAE v4.0) of Grade 2 or higher: congestive heart failure, dyspnea, edema, or arrhythmia, a decrement in left ventricular ejection fraction on echocardiogram $> 10\%$ from baseline (per central review) or to less than 53% absolute, or an increase in global longitudinal strain (GLS) by $> 15\%$ from baseline (per central review), the proportion of patients experiencing cardiovascular toxicity at any time while on study will be compared between the two treatment arms. [\(33\)](#) Assuming a clinically relevant cardiovascular toxicity rate of 8% in the control arm, a binomial test with a one-sided significance level of 0.1 and 63 eligible patients in each arm has 79% power to detect a difference of 15% between arms. Furthermore, a multivariate Cox Proportional Hazards model estimating time-to-clinically significant cardiovascular toxicity will be developed using a stepwise selection procedure and will consider potentially relevant baseline factors including patient demographic data, comorbid conditions, clinical data, echocardiography and serum biomarkers, where a clinically significant cardiotoxicity is defined as Grade 2 or greater cardiac toxicity per CTCAE v4.0, following subclinical myocardial dysfunction, as defined by abnormalities in LV strain (an increase of GLS $> 15\%$) and/or in serum biomarker levels (NTproBNP, BNP, CKMB, Troponin T, or Troponin I levels that are greater than the upper limit of normal from the reference range of the testing laboratory). All patients who are eligible and who have been assessed for toxicity will be included in the above described analyses. Additionally, the timing and onset of clinically significant cardiotoxicity from the onset of the earliest occurrence of subclinical myocardial dysfunction will be evaluated using cumulative incidence analysis. All patients who are eligible, who have been assessed for toxicity, and who have developed a subclinical abnormality will be included in this analysis.

All these analyses will be exploratory and hypothesis-building as there are not enough patients to perform meaningful hypothesis testing. However, this will be a unique opportunity to study this subset of patients.

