10.0 CRITERIA FOR EVALUATION AND ENDPOINT ANALYSIS

10.1 Response Criteria

Multiple Myeloma:

For the purpose of establishing one set of criteria for both Phase II and Phase III multiple myeloma studies, the following definitions will be used. These definitions are based on the International Uniform Response Criteria for Multiple Myeloma.

a. **Measurable Disease:** Measurable, quantifiable protein criteria must be present. Acceptable protein criteria are:

- Serum M protein ≥ 1 g/dL (≥ 10 g/L), quantified by using densitometry on serum protein electrophoresis (SPEP).

AND / OR

- Urine M protein [Bence-Jones Protein] ≥ 200 mg/24 hrs (≥ 0.2 g/24 hrs), quantified by 24-hour urine protein electrophoresis (UPEP, see Section [10.2.b](#)).

AND / OR

- Bone marrow plasma cells $\geq 30\%$

OR

- Patients who have both serum M protein levels < 1 g/dL AND urine M protein levels < 200 mg/24 hrs at baseline may be followed by serum free light chain (FLC) assay if involved free light chain level ≥ 10 mg/dL (≥ 100 mg/L).

Oligosecretory and Non-secretory Disease: Patients that do not meet the criteria for measurable disease above will be ineligible for this study.

b. **Objective Status:**

Stringent Complete Response (sCR):

- Meets all of the criteria for Complete Response (CR) and
- normal serum free light chain ratio and
- absence of clonal cells in bone marrow by immunohistochemistry or immunofluorescence

Complete Response (CR):

- Disappearance of all evidence of serum and urine M proteins on immunofixation electrophoresis studies **and**
- $< 5\%$ plasma cells in bone marrow **and**
- disappearance of any soft tissue plasmacytomas

Very Good Partial Response (VGPR):

- Meets all of the criteria for Partial Response (PR) **and**
- Serum and urine M proteins detectable by immunofixation but not on electrophoresis **or**
- $\geq 90\%$ reduction in serum M protein and urine M protein < 100 mg/24 hrs.

Partial Response (PR):

- If the patient had soft tissue plasmacytomas present at baseline and they were assessed at this disease assessment: $\geq 50\%$ reduction in size of soft tissue plasmacytomas (see Section [10.2.h](#)) **and**
- If the patient had $\geq 30\%$ plasma cells in bone marrow at baseline and a bone marrow biopsy was done: $\geq 50\%$ reduction in plasma cells **and**
- $\geq 50\%$ reduction in serum M protein and reduction in urine M protein $\geq 90\%$ or to $< 200 \text{ mg/24hr}$ **or**

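### Section 11.6 predicts CR by PET from the Section 10.1 CR, which already requires plasmacytomas to disappear, so a positive association is built in by definition

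*Combined protocol and SAP*

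**What the plan says.** Section 11.6 names as the main focus of the PET work the "association of biochemical response with PET response for patients presenting with EMP at baseline". The planned method is univariate and multivariate logistic regression "to determine the impact of biochemical CR as defined in Section" 10.1 on CR by PET. The predictor is thus defined by cross-reference. The outcome, CR by PET, is defined as "the disappearance of all focal lesions and the resolution of EMD".

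Section 10.1 CR has three parts, all required: "Disappearance of all evidence of serum and urine M proteins on immunofixation electrophoresis studies", fewer than 5% plasma cells in the marrow, and "disappearance of any soft tissue plasmacytomas".

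Four further places bear on the point:

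- Section 2.0 (FDG-PET background) describes biochemical response as something measured in serum and/or urine.
- Section 11.6 times the second PET at VGPR or better, or at the end of cycle 12, whichever is earlier. It adds: "This second PET image will help determine response in those patients".
- The study calendar (Section 9.0) schedules no soft tissue imaging other than FDG-PET.
- Section 11.6 closes by calling its analyses exploratory, with too few patients for meaningful hypothesis testing.

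**The concern.** The analysis is confined to patients who have extramedullary disease at baseline, so the plasmacytoma part of the CR definition applies to essentially all of them. Clearing that disease is needed both to be a CR in the predictor and to be a CR in the outcome. The regression would therefore tend to show an association even if M-protein response and PET response had nothing to do with each other.

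Objective 1.3b is to explore PET as a tool for assessing treatment response. With a contaminated predictor, a positive finding cannot be read as evidence that PET and biochemical response agree. More patients would not remove the bias, nor would adjustment for age, albumin and the other listed covariates. The primary endpoint and the response-rate endpoint are not affected.

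**Working it through.** The plan gives no effect size, power or expected CR rate for this analysis, so it has no figure of its own to reproduce. I compare the definitions, then illustrate the consequence with assumed rates.

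**Definitions side by side**

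| Component | Section 10.1 CR (predictor) | CR by PET (outcome) |
|---|---|---|
| Negative serum and urine immunofixation | required | not required |
| Under 5% marrow plasma cells | required | not required |
| Extramedullary / soft tissue disease gone | required | required |
| All other focal lesions gone | not required | required |

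The plasmacytoma part of the PR definition in 10.1 applies only if the lesions were assessed on that occasion. The CR definition carries no such condition.

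**Model (all rates assumed)**

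- B: M-protein and marrow CR, probability b.
- S: soft tissue disease resolved, probability s.
- F: all other PET foci resolved, probability f.
- B, S and F are independent, so biochemical and PET response are truly unrelated.
- Predictor CR = B and S. Outcome PET CR = S and F.

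Then:

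- P(PET CR | CR) = f
- P(PET CR | no CR) = sf(1 − b)/(1 − bs)
- Risk ratio = (1 − bs)/(s(1 − b)), which exceeds 1 whenever 0 < s < 1.

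**Example: b = 0.2, s = 0.5, f = 0.8**

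- P(PET CR | CR) = 0.80.
- P(PET CR | no CR) = 0.5 × 0.8 × 0.8/(1 − 0.1) = 0.32/0.90 = 0.36.
- The four cells are 0.08 (CR, PET CR), 0.02 (CR, no PET CR), 0.32 (no CR, PET CR) and 0.58 (neither).
- Odds ratio = (0.08 × 0.58)/(0.02 × 0.32) = 7.25.

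**Range over b = 0.1–0.5, s = 0.3–0.7, f = 0.6–0.8**

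Let k be the share of patients whose 10.1 soft tissue assessment is independent of the PET reading. The probability that both assessments show resolution is then (1 − k)s + ks².

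| b, s, f | PET CR in CR vs no CR (k = 0) | OR, k = 0 | OR, k = 0.5 | OR, k = 1 |
|---|---|---|---|---|
| 0.1, 0.7, 0.6 (lowest) | 0.60 vs 0.41 | 2.19 | 1.48 | 1.00 |
| 0.2, 0.5, 0.8 | 0.80 vs 0.36 | 7.25 | 2.47 | 1.00 |
| 0.5, 0.3, 0.8 (highest) | 0.80 vs 0.14 | 24.33 | 4.60 | 1.00 |

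**What a sample would show**

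This uses the example rates with k = 0, 20,000 simulated samples, and a one-sided Fisher test at an assumed level of 0.1. Section 11.6 expects 16 to 32 patients with EMP.

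| n | No CR patient at all | Sample OR above 1 | p ≤ 0.1 |
|---|---|---|---|
| 16 | 18% | 71% | 12% |
| 32 | 3% | 90% | 34% |

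**After the fix**

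With predictor B alone, the joint probability with PET CR is b × sf, the product of the margins. The odds ratio is exactly 1.00 under the same model, so the plasmacytoma criterion is the source of the artefact.

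**The case against.** The strongest reply is that the intended meaning is clear. Section 11.6 says biochemical CR rather than CR, Section 2.0 ties biochemical response to serum and urine, and Section 10.3 describes an unconfirmed CR as resting on serum and urine studies plus marrow if drawn. On that reading the cross-reference is merely loose. This explains what was probably meant, but Section 10.1 contains no serum-and-urine-only CR. An analyst who follows the reference gets the contaminated variable.

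A second reply is that the two definitions differ, and this largely stands:

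- A patient can meet the 10.1 CR and keep a skeletal focus on PET.
- The second PET may be taken at VGPR, before a later CR.
- Section 10.1 names no imaging method. Section 10.2g sizes plasmacytomas by cross-diameters, whereas Section 15.1 reads PET qualitatively and by SUVmax.

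A reader might therefore infer too much from the overlap: that an association is guaranteed, the odds ratio near infinite, and CR without PET CR an almost empty cell. The documents do not support that. It would require plasmacytoma clearance to be the same event as CR by PET (f = 1 in the model above), which ignores the requirement that all focal lesions clear.

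Third, the analysis is exploratory, small, and not the only PET analysis: Section 15.1 also plans categorical PET response and SUV as a continuous measure. That limits the consequence. It excuses low power, but not a predictor that contains part of its outcome.

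**Conclusion.** The point holds in a limited form. Following the cross-reference in Section 11.6 puts extramedullary resolution on both sides of the regression, and the definitions build in a positive association in expectation. How large it is cannot be read from the documents. Under independence with a fully shared soft tissue assessment, the odds ratio is about 2 to 24 over the assumed rates. With half of the patients assessed independently it is about 1.5 to 4.6, and with unrelated assessments it is 1. Substantial sharing is plausible, because FDG-PET is the only scheduled soft tissue imaging and 11.6 says the second scan helps determine response, but the plan does not settle it. With 16 to 32 patients the bias may or may not show in the data. Only the exploratory PET objective is affected, but there a positive result would not be interpretable as written.

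**What to change.** In Section 11.6, define biochemical CR for this analysis as negative serum and urine immunofixation, with under 5% marrow plasma cells where a marrow was done, and without the plasmacytoma criterion. This also brings the section closer to the serum and urine meaning in Section 2.0.

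State the timing of biochemical CR relative to the second PET: status at the assessment nearest the scan, or best response on treatment. The choice matters because a scan triggered at VGPR can come before the CR.

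Keep the full Section 10.1 CR for the response-rate endpoint.

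The cost is a clause or two of text. Serum and urine immunofixation is already scheduled for each of Cycles 2 to 12, and closure to accrual does not prevent the change. The downside is that the predictor in this one exploratory analysis will differ from the protocol's formal CR, which the report should say.

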11.2 Sample Size and Power Justification

Sixty-three eligible patients will be accrued to each treatment arm unless undue toxicity is encountered. The study anticipates an accrual of 72 eligible patients per year, based on recent ECOG accrual estimates for intergroup trials in this patient population. Thus 126 patients will be accrued in approximately 1.75 years. The study anticipates accruing an additional 14 patients to account for ineligibilities and withdrawal of consent for a total of 140 patients.

A median PFS of 9 months is anticipated in Arm 1, based on previous trials using this treatment combination in this patient group (Onyx, personal conversations). With 1.75 years of patient accrual and 1.5 years of follow-up 63 patients per arm results in a study with 90% power to detect a hazard ratio of 1.67, which corresponds to an increase in median PFS from 9 months to 15 months in Arm 2, the arm with the higher carfilzomib dose. These calculations are based on a one-sided stratified log rank test at level (alpha) of 0.1 and on the assumption that progressions are exponentially distributed.

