15.0 SPECIAL INSTRUCTIONS

15.1 FDG-PET Imaging (mandatory)

A standard FDG-PET scan will be obtained for all patients at the time of study entry and patients who have evidence of extramedullary progression (EMP) will have a second PET scan at the end of treatment or at the time of achieving a VGPR or better response, whichever occurs earlier. Note: The baseline PET scan may have been obtained as part of standard of care (prior to patient informed consent) provided that it was obtained within 28 days prior to registration. The follow up PET scan should occur at least 2 weeks after the last dose of study treatment received.

The funding of the second PET scan will be provided by the sponsor for the first 30 patients. Upon confirmation of receipt of the first 30 scans, a memorandum will be sent to investigators advising that no further patients should have PET scans submitted and that sites may remove the extra PET scan from their local consent forms.

Images will be submitted for central review via AG Mednet as outlined in Appendix [18.2](#) and will be reviewed by the PET Coordinator as outlined in Section [11.6](#).

Sites should obtain the AG Mednet Desktop Agent at the time of IRB approval (see Appendix [18.2](#)). Note that users must request access for this trial even if AG Mednet is being used for another SWOG trial.

FDG-PET studies will be acquired per standard clinical protocol. All studies will be performed as PET/CT, with inclusion of a dose-optimized CT study for attenuation correction and localization. The following scan parameters will be recorded at each site: administered activity (mCi), localization time (min), and injection site. Scans will include the whole body, from the vertex of the skull to the feet in order to include the entire skeleton.

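### The covariate-adjusted PET model in Section 11.6 has at least seven predictors, if all are entered, for about 13-28 patients: often inestimable at about 20 or fewer, overfitted otherwise

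*Combined protocol and SAP*

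**What the plan says.** The imaging part of Section 11.6 states as its main aim to "determine the association of biochemical response with PET response for patients presenting with EMP at baseline". The method is given as follows: "Univariate and multivariate logistic regression will be used to determine the impact of biochemical CR as defined in Section" 10.1 on CR by PET. The multivariate model is then described in a sentence that begins "In the multivariate analysis adjustment for standard prognostic factors such as age, albumin" and whose full commitment is: "adjustment for standard prognostic factors such as age, albumin, β -2 microglobulin, serum creatinine, CRP and LDH will be included".

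On the size of the analysis set, the same section says: "It is expected that 10-20% of patients (approximately 16-32 patients) will have EMP". Section 11.2 gives the planned trial size: "Thus 126 patients will be accrued in approximately 1.75 years", and "The study anticipates accruing an additional 14 patients to account for ineligibilities and withdrawal of consent for a total of 140 patients". Section 15.1 adds a ceiling: "The funding of the second PET scan will be provided by the sponsor for the first 30 patients", after which no more PET scans are to be submitted.

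Section 11.6 gives no expected rate of biochemical CR or of PET CR. It names no penalised or exact method, no limit on the number of covariates and no rule for sparse data. It ends by calling all its analyses exploratory and conceding that there are too few patients for meaningful hypothesis tests.

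**The concern.** Biochemical CR plus six named covariates makes seven slopes and an intercept, and the wording *such as* allows more. The model is to be fitted to a subgroup of perhaps two dozen patients, of whom only some will have a PET CR.

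Two things can go wrong. If some combination of predictors splits the PET-CR patients from the rest (complete or quasi-complete separation), maximum likelihood has no finite solution, and software prints an arbitrary large odds ratio with a meaningless interval. If the data are not separated, an estimate exists, but it is fitted to fewer events than is reasonable for seven slopes.

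With no rule written down, the analyst would have to choose which covariates to drop after seeing the data. What is at stake is the adjusted odds ratio between biochemical and PET response, an exploratory result under the objectives of Section 1.3.

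**Working it through.** **1. The plan's own figure.** 16/0.10 = 160 and 32/0.20 = 160, so the printed 16-32 rests on 160 patients. From the planned sizes in Section 11.2:
- 126 eligible: 0.10 x 126 = 12.6 to 0.20 x 126 = 25.2
- 140 in total: 0.10 x 140 = 14 to 0.20 x 140 = 28

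The analysis set is therefore about 13-28 patients. The printed upper end of 32 also exceeds the 30 second scans after which Section 15.1 stops submission.

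**2. Predictors.** One (biochemical CR) + six (age, albumin, beta-2 microglobulin, creatinine, CRP, LDH) = 7.

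**3. Events per predictor**, n x (PET-CR rate)/7. PET CR of 20-40% is an assumption.
- Lowest: 13 x 0.20/7 = 0.37
- Highest: 28 x 0.40/7 = 1.60
- Most favourable reading of the printed range: 32 x 0.50/7 = 2.29

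**4. A closed-form check on separation.** For seven continuous predictors and a random 50:50 outcome, the chance of complete separation is the sum over k = 0 to 7 of C(n-1, k)/2^(n-1). This gives 81% at n=13, 50% at n=16, 18% at n=20, 1% at n=28 and 0.2% at n=32. An evenly split outcome is a favourable case.

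**5. Simulation under less favourable rates.** Assumptions: biochemical CR 30%, PET CR 20-40%, six independent normal covariates, no true effects. A linear programme checks each data set for complete or quasi-complete separation; data sets with a constant outcome or constant biochemical CR also count as having no estimate.

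To see how much is due to the covariates, the table adds the chance that the plain 2x2 table has an empty cell. With independent margins and cell probabilities c, this is the sum of (1-c)^n over the four cells, less the sum over pairs of cells of (1-c-c')^n, plus the sum of c^n. Example at n=28 with PET CR 20%: the cells are 0.06, 0.24, 0.14 and 0.56; 0.94^28 + 0.76^28 + 0.86^28 = 0.177 + 0.000 + 0.015 = 0.192; the pair terms (mainly 0.8^28 = 0.002) bring it to 0.19.

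| n | Full model has no finite estimate | 2x2 table has an empty cell |
|---|---|---|
| 13 | 88-95% | 27-55% |
| 16 | 55-85% | 17-44% |
| 20 | 25-64% | 10-33% |
| 28 | 4-30% | 3-19% |

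In each range the higher figure belongs to PET CR 20% and the lower to 40%. At n=20 or below the covariates add greatly to the problem. At n=28 most of it is already in the 2x2 table. At n=32 separate runs gave 23, 6 and 2% with the covariates and 15, 5 and 2% without, for PET CR of 20, 30 and 40%.

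**6. Wider assumptions.** With biochemical CR 10-50%, PET CR 20-50% and odds ratios of 1 or 5, the share with no finite estimate was 80-98% at n=13, 49-95% at n=16, 20-86% at n=20, 2-66% at n=28 and 0-62% at n=32. The high end at n=28 and 32 needs biochemical CR as low as 10%.

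**The case against.** The strongest reply has four parts.

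- **The plan is not only the adjusted model.** A univariate logistic model with one binary predictor gives the same odds ratio as the 2x2 table. Section 15.1 also plans qualitative PET response, response by change in SUVmax, and SUV as a continuous variable. This stands. A reader might infer that the plan leaves no usable PET analysis; the documents do not support that.
- **The wording is looser than a fixed seven-predictor fit.** *Such as* can be illustrative, and Section 11.6 does not prescribe unpenalised maximum likelihood. This stands in part: a Firth or exact fit would be compatible with the text. But the text commits to including adjustment for such factors, names six, and gives neither a limit nor an estimation method suited to sparse data.
- **Sparse data are a problem with or without covariates.** This stands at n of about 28-32. An exact odds ratio is also zero or infinite when a cell is empty. Its interval, however, remains valid and is simply open on one side.
- **The plan already calls these analyses exploratory and the sample too small.** This limits the importance of the point. It does not make the stated model estimable, since the concession is about hypothesis testing and leaves the model in place.

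**Conclusion.** The point holds for the adjusted model. If all six factors are entered, the adjusted odds ratio is often inestimable at about 20 patients or fewer and overfitted otherwise. Events per predictor are about 0.4-1.6 under the assumed rates, and at most 2.3 even at n=32 with 50% PET CR.

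How often estimation fails depends on CR rates that the documents do not give: PET CR of 20-40% and biochemical CR of 30% are assumptions, as are the independent null covariates. It would be wrong to read the result as certain failure. At n=28 the figure is 4-30%, and it is about 2% if both rates are near 50%. The roughly 90% figure applies at n=13, below the plan's printed lower bound of 16.

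The mismatch between 16-32 and the trial's size is a plain arithmetic error and needs no assumption; the conclusion on overfitting is the same on either range. No primary or secondary conclusion uses this model, so this is a correction worth making, not a threat to the trial.

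**What to change.** In Section 11.6:

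1. Make the unadjusted association of biochemical CR with PET CR the analysis. Report it as a 2x2 table with an exact odds ratio and confidence interval, one-sided if a cell is zero.
2. Replace the multi-covariate model with Firth-penalised (or exact) logistic regression limited to one covariate, named before the PET responses are analysed, and label it exploratory.
3. Correct the expected number of patients with EMP from 16-32 to about 13-28.

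The cost is a few sentences. The downside is that there will be no fully adjusted odds ratio, which samples of this size could not reliably supply. One covariate is a cautious choice rather than the only defensible one; what matters is that the limit and the method are fixed in advance.
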